6.2 Reporting to the Ethics Committee

The sponsor will assess whether any relevant safety information that becomes available during the study should be reported ad hoc to the Ethics Committee of the University Hospitals Leuven, Belgium.

The sponsor has the obligation to, once a year throughout the clinical trial (or on request), submit a progress report to the Ethics Committee of the University Hospitals Leuven, Belgium containing an overview of all serious adverse events that occurred during the reporting period and taking in to account all new available safety information received during the reporting period.

7. Statistics

7.1 Sample size

Although this is a pilot study, we have calculated our sample size based on the data on SARS-CoV-2 positive Belgian citizens (58 517 011, data from Sciensano, bulletin of the 1st of May 2020) with a confidence interval of 5 and a confidence level of 95%. This will be the largest investigated cohort so far.

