perception of anosmia and/or ageusia. Especially this anosmia part might be interesting. A correlation between anosmia and a positive PCR in the tear film is suspected based on the connection between the nose and eyes via the nasolacrimal duct and the proximity of the olfactory nerve to the orbital cavity and eye.

The other parts of our study aims to confirm the detectability of the SARS-nCoV-2 virus in the tear film of **pauci-symptomatic** volunteers, more specifically patients presenting at the emergency room of the University Hospitals Leuven, health care workers with mild symptoms and patients admitted for other reasons though SARS-nCoV-2 positive.

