Presumably, the rate of pauci-symptomatic carriers is higher within health care workers compared to the general population. Emergency patients and health care workers are preferred over pauci-symptomatic pre-operative patients, since prevalence of SARS-nCoV-2 is low in these pre-operative patients (data UZ Leuven Laboratory Medicine (1 June 2020): prevalence of around 0.2%). Similar to the symptomatic patients, all volunteers will be informed about our project and asked to sign an informed consent for simultaneous swabbing of the conjunctiva and the nasopharynx. The pauci-symptomatic group will include only volunteers already listed for nasopharyngeal swabbing based on their symptoms (to avoid unnecessary use of nasopharyngeal swabs). By testing pauci-symptomatic volunteers, we intend to better substantiate current guidelines in ophthalmology practice. Mostly “deemed-healthy” patients visit outpatient clinics, but when carrying the virus, they are the highest risk of contaminating health care workers. Proving presence of (viable) SARS-nCoV-2 virus in the tear film of pauci-symptomatic volunteers might change our ophthalmology practice in the long run. Furthermore, we want to compare results of both the ocular and nasopharyngeal swab (both positive for SARS-nCoV-2; both negative for SARS-nCoV-2; discordant results, with either eye or nasopharynx positive and the corresponding sample negative for SARS-nCoV-2). For patients with discordant results, we purpose to identify potential correlations between disease-severity and detection of SARS-nCoV-2 in different body fluids by using the same questionnaire mentioned above (*cf. Addendum A*). The difference in RNA viral load (by means of quantitative result (Cycle threshold (Ct) of the SARS-CoV-2 PCR) in the tears of different patients at different moments in time (i.e. the assessment of the evolution of quantitative result) will be indicative for the transmissibility of the virus. However, to evaluate genuine transmissibility, swabs positive for SARS-CoV-2 via qPCR will be sent to the REGA institute (i.e. the Laboratory of [name]) for **viral culture and detection of subgenomic (sg) RNA**. This is in contrast to most previously published studies focusing only on the detection of SARS-CoV-2 RNA by PCR. SARS-CoV-2 PCR is not able to differentiate between live or dead virus (6–8). It is important to make that difference in order to draw conclusions on potential transmission of the virus by tears. Detection by culture indicates if viable virus is present in the sample. Detection of sgRNA is an indicator for replication of the virus. The viability of the virus collected from tear samples will determine the risk of spreading the virus via tears.

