
Tear film SARS-nCoV-2 detection in symptomatic and pauci-symptomatic patients.

This research project intends to provide a more thorough understanding of the presence of this new virus in the tear film of SARS-nCoV-2 positive patients. Furthermore, it could provide insight in the timing of the contagiousness of tears and highlights correlations with other signs and symptoms.

[figure not shown]

Figure 1: study design.

2. Trial objectives and design

Primary outcome measures

- 1) The presence of SARS-nCoV-2 in the tear film of symptomatic and pauci-symptomatic SARS-nCoV-2 positive patients.
- 2) Correlations between SARS-nCoV-2 in the tear film and mild (like anosmia, ageusia, upper and lower respiratory tract infection) or severe symptoms (as pneumonia, need for hospitalization) of COVID-19.

Secondary outcome measures

- 1) The stage of disease when SARS-nCoV-2 becomes detectable in the tears.
- 2) Duration of shedding of SARS-nCoV-2 RNA in the tears.
- 3) Difference in RNA viral load (by means of quantitative result (Cycle threshold (Ct) of the SARS-nCoV-2 PCR) in tears of different patients at different moments in time in order to estimate potential difference in transmissibility of the virus by tears.
- 4) Assessment of evolution of quantitative result (Cycle threshold (Ct)) of the SARS-nCoV-2 PCR over time within conjunctival SARS-nCoV-2 PCR positive patients
- 5) Searching for a correlation between both quantitative and qualitative results of SARS-nCoV-2 PCR on the nasopharyngeal and conjunctival swab (both positive for SARS-nCoV-2; both negative for SARS-nCoV-2; discordant results, with either eye or nasopharynx positive and the corresponding sample negative for SARS-nCoV-2).

Tear film SARS-nCoV-2 detection in symptomatic and pauci-symptomatic patients.

- 6) Exploring the possibility of testing the tear film on SARS-nCoV-2 as a screening tool for early disease.
- 7) Exploring the replication of the SARS-nCoV-2 virus, by differentiating between death and alive SARS-nCoV-2 virus through sg RNA-testing and tissue culture.

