2.1 Preparation, organization and management of this exploratory study

Part 1: Serial sampling of symptomatic and confirmed positive patients

Patients will be informed about the study by a health care worker at a non-ICU unit (“rampen unit”) of the University Hospitals Leuven, Belgium.

In case a candidate is interested in participating and tested positive for SARS-nCoV-2 on his/her nasopharyngeal swab, he/she will be informed about the study goals by the same health care worker. The volunteer will receive an information letter and a copy of the informed consent to take home.

Study procedure

After signing the informed consent, each patient will be asked to fill in a questionnaire (cfr. *Addendum A*).

The simplicity of performing a conjunctival swab makes it possible **to implement in the daily routine** of health care workers, **avoiding additional waste of personal protective equipment.**

Conjunctival sampling will be performed on both eyes after the application of a drop of topical anesthesia (Minims® Oxybuprocaine Hydrochloride 0.4%, Bausch and Lomb, Aubenas, Frankrijk). A timed 5 minutes will be in between application of the drop and the sampling. The sampling will be performed by a trained nurse and/or medical student and/or resident after proper training of correct sampling (cfr *Addendum B*).

Each eye will be sampled with a single, sterile, nylon, flocked swab (FLOQSwabs®; Copan, Brescia, Italy). This FLOQSwabs® is a **different** swab than the one used for routine nasopharynx SARS-nCoV-2 testing.

The sampling will be done from the nasal to temporal inferior conjunctival sac, the swab will be swirled in the opposite direction of the sampling itself.

The swabs will be placed in a tube with universal transport medium (UTM) and transferred to a -80°C freezer until further processing.

The conjunctival swab will be tested for SARS-nCoV-2 presence by making use of in-house reverse transcription real-time polymerase chain reaction (RT-PCR) designed for routine diagnostics targeting specific SARS-nCoV-2 genes in the clinical laboratory of the University Hospitals Leuven or at the REGA institute (laboratory of [name]).

Tear film SARS-nCoV-2 detection in symptomatic and pauci-symptomatic patients.

Serial sampling

Sampling will be repeated every 3 days to evaluate if PCR becomes positive during the course of disease and to monitor the duration of detectability of the virus in tears.

Part 2: Single sampling of pauci – symptomatic patients

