
Emergency patients, health care workers and patients hospitalized for a different condition/reason with a limited amount of symptoms (cfr. Inclusion criteria) that apply for a nasopharyngeal swab to confirm COVID-19 will be informed about the study by a pre-indicated health care worker.

When the patient is interested in participating he/she will be informed about the study goals by the same health care worker. The volunteer will receive an information letter and a copy of the informed consent to take home.

After signing the informed consent, each patient will be asked to fill in a questionnaire (cfr. *Addendum A*).

Study procedure

The conjunctival swabbing has been explained in detail in part 1.

3. Selection and withdrawal of subjects

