3.1 Inclusion criteria

- Subject needs to be above 18 years old.
- The subject is willing to undergo sampling of the conjunctiva.
- The subject is willing to fill in a questionnaire.
- The subject is fluent in written and verbal Dutch.
- The subject is capable of giving informed consent.
- Applicable for part 1 only: the subject test positive for SARS-nCoV-2 on a nasopharyngeal swab. The time window between a positive nasopharyngeal swab and the first conjunctival swab may be no more than 3 days.
- Applicable for part 2 only: mild symptoms of COVID-19 including symptoms of upper or lower respiratory tract infection and/or any body temperature elevation (criteria Sciensano for testing healthcare workers (April 12 2020)) without the need for hospitalization.

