4.1 Summary of visits

Part 1: Serial sampling of symptomatic patients

Sampling will take place at the “rampen unit” of the University Hospitals Leuven, Belgium. Once the patient is admitted and tested positive for SARS-nCoV-2 on nasopharyngeal swab, conjunctival sampling will take place every three days until the day of discharge. The time window between a positive nasopharyngeal swab and the first conjunctival swab may be no more than 3 days.

Part 2: Single sampling of pauci-symptomatic patients

Sampling will take place at the emergency department of the University Hospitals Leuven, Belgium by the swab team. The sampling will not be repeated.

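### Does the unstated sample size in section 7.1, with no confidence interval named in 7.2, call for a change to the plan?

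*Combined protocol and SAP*

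**What the plan says.** Section 7.1 takes as its basis "SARS-CoV-2 positive Belgian citizens (58 517 011, data from Sciensano, bulletin of the 1st of May 2020) with a confidence interval of 5", at 95% confidence, and describes the study as a pilot. It reports no n. No other readable part (synopsis, objectives, procedures, eligibility, addenda) gives a target number. Figure 1, the study design, is not shown and might carry one.

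The first primary outcome in section 2 is "The presence of SARS-nCoV-2 in the tear film of symptomatic and pauci-symptomatic SARS-nCoV-2 positive patients". Part 1 requires a positive nasopharyngeal swab. Part 2 enrols on symptoms (section 3.1: "Applicable for part 2 only: mild symptoms of COVID-19 including symptoms of upper or lower respiratory tract infection and/or any body temperature elevation"). Section 2.1 says that people "that apply for a nasopharyngeal swab to confirm COVID-19 will be informed about the study by a pre-indicated health care worker", and section 1 says that volunteers are "asked to sign an informed consent for simultaneous swabbing of the conjunctiva and the nasopharynx". Section 1 also lists "patients admitted for other reasons though SARS-nCoV-2 positive" in the pauci-symptomatic group.

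On sampling, section 2.1 states: "Conjunctival sampling will be performed on both eyes after the application of a drop of topical anesthesia". For Part 1, section 4.1 states that "conjunctival sampling will take place every three days until the day of discharge"; Part 2 is sampled once.

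Section 7.2 summarises categorical variables by count and percentage, sets a P-value threshold of 0.05 for tests, and does not mention confidence intervals.

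**The concern.** A precision statement is the only planning property the protocol offers, and a reader cannot reproduce it. The two missing inputs, the meaning of 5 and the assumed proportion, are the ones that determine n.

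The denominator adds a second doubt. The primary outcome concerns positive patients, yet Part 2 can enrol people whose nasopharyngeal result is still unknown. If n meant total enrolment, those who test negative would not contribute to the primary proportion, and its precision would be worse than planned.

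Third, 7.1 plans for an interval that 7.2 does not promise to report. If positivity in tears is low or zero, a bare percentage could be read as stronger reassurance than the data support. Finally, with two eyes and serial swabs in Part 1, counting swabs instead of patients would make any interval too narrow.

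**Working it through.** **Inputs.** From section 7.1: confidence 95% (z = 1.96, taken as two-sided), precision 5 (unit not given), population 58 517 011. From section 7.2: counts and percentages. Assumed, because not stated: proportion p and the share of enrolled people who are positive. The readable text states no n, so there is no planned figure to reproduce.

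**1. What 7.1 implies.** n0 = z² p(1−p)/d².
- Half-width 5 points, p = 50%: 3.8416 × 0.25 / 0.0025 = 384.16, so 385.
- Full width 5 points (d = 0.025), p = 50%: 3.8416 × 0.25 / 0.000625 = 1,536.64, so 1,537.
- Half-width 5 points at p = 20%, 10%, 5%: 246, 139, 73.

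The unit and p therefore drive n. The familiar convention (plus or minus 5 points, p = 50%) gives 385, but the protocol does not state that number.

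**2. Does the population figure matter?** n = n0 / (1 + (n0 − 1)/N).
- N = 58,517,011: 384.16, so 385.
- N = 58,517: 384.16 / (1 + 383.16/58,517) = 381.66, so 382.

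The difference is 3 patients. The printed figure is too large for a count of positive citizens (2.9 times an assumed national population of 20 million), but it may come from reading the file, and n hardly depends on it.

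**3. Does the denominator matter?** Wilson half-width = z/(1 + z²/n) × √(p(1−p)/n + z²/(4n²)).

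| Positive patients | p = 50% | 20% | 10% | 5% |
|---|---|---|---|---|
| 385 | 4.97 | 3.99 | 3.01 | 2.21 |
| 192 (half of 385) | 7.00 | 5.63 | 4.27 | 3.18 |

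If 385 counts positive patients, plus or minus 5 points is met at every p. If 385 is total enrolment and half are positive, it is met only for p up to about 15%. If the sponsor had planned at p = 5% (n = 73), the half-width at p = 50% would be 11.2 points. Each result depends on an n that the documents do not give, so none shows that a stated precision is missed. The reference population in 7.1 is positive people, which favours the first row.

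**4. Is the interval lost?** It needs only the count and the denominator.
- 10 of 100: Wilson 95% interval 5.5% to 17.4%.
- 0 of 50: exact upper limit 1 − 0.025^(1/50) = 7.1%.
- 0 of 100: 1 − 0.025^(1/100) = 3.6%.

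The count and percentage in 7.2 supply both quantities.

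**5. Unit of analysis.** If 2 eyes × 3 visits were treated as 6 independent records, the design effect would be 1 + 5ρ: 2.5 at ρ = 0.3 and 5.0 at ρ = 0.8. Intervals would be too narrow by √2.5 = 1.6 to √5.0 = 2.2 times. The plan proposes no such analysis. Section 2 frames the outcome in patients, and the onset and duration of detectability in tears are separate secondary outcomes.

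**The case for a change.** The best case for a change is that 7.1 raises its pilot status and still claims a calculation, so pilot status does not excuse leaving out the result. An interval around a low or zero proportion matters in a study that hopes to inform ophthalmic practice. The remedy would take a few sentences and need not enrol anyone extra.

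Much of this stands as a comment on reporting. The calculation cannot be reproduced from the readable text. Two conventions are also open: whether the first visit or any visit counts in Part 1, and how a patient positive in the eye but negative in the nasopharynx is classed. The first can affect the result: 5% positivity per visit becomes anything from 5% to 1 − 0.95³ = 14.3% over three visits, depending on how far the visits are dependent.

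What does not stand is the step from silence to defect. Section 7.2 does not exclude intervals. Discordant results have their own secondary outcome, so they will be shown whichever convention is used. An analyst working per patient, with Part 1 and Part 2 identified, can state the visit rule and attach an interval from data already planned. Reporting intervals by Part alone would not settle the matter either, because 7.1 claims no precision per Part.

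**Conclusion.** No change follows. The gap is real: n, the unit of 5 and the assumed proportion are missing from the readable text, and no interval is named for the primary proportion. But it is incomplete reporting, not an arithmetic error, and the documents give no n against which a shortfall could be shown. The spread of 385 to 1,537 at p = 50% measures how ambiguous one sentence is, not a loss of precision in the study. The population figure accounts for at most 3 patients on the conventional reading. Followed as written, the analysis yields the numbers from which a reader can compute the interval.

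This rests on three assumptions: that the primary proportion is counted per patient, as section 2 words it; that the denominator and the visit rule are stated with the result; and that the study is read as the pilot it says it is. Figure 1 might also supply the missing n.

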7.2 Analysis

The statistical analyses will be performed using statistical software such as R-studio or SPSS. The Shapiro-Wilk test will be used for normality testing. Depending their distribution, continuous variables will be summarized as mean \pm standard deviation or median with interquartile range. Categorical variables will be summarized in absolute numbers and percentages. All statistical test will be significant if the P-value ≤ 0.05 .

Primary outcome measures

The presence or absence of the virus in the tears is the primary objective. A multivariate analysis will be used to interpret the questionnaire.

Secondary outcome measures

Tear film SARS-nCoV-2 detection in symptomatic and pauci-symptomatic patients.

For secondary outcome measures, we first have to indicate the different disease stages. We define them as early, intermediate and late stadium, respectively indicated by onset disease symptoms (cough, fever, fatigue, myalgia and lesser reported symptoms such as headache, diarrhea and abdominal pain, ageusia and anosmia, conjunctivitis), development of chest pains and dyspnea with need for hospitalization and eventually development of SARS and need for ICU administration (12). We also define a remission stage in which symptoms start to decline.

For investigation of the disease stage in which the SARS-nCoV-2 becomes detectable in the tears we aim to use an ANOVA analysis.

8. Quality assurance

To assure maximal quality and reproducibility, the trial protocol will be followed rigorously.

9. Direct access to source data and documents

Only data gathered in the context of the trial will be used.

10. Ethics and regulatory approvals

The trial will be conducted in compliance with the principles of the Declaration of Helsinki (2008), the principles of Good Clinical Practice and in accordance with all applicable regulatory requirements. This protocol and related documents will be submitted for review to Ethics Committee of the University Hospitals Leuven.

The Study will be conducted only on the basis of prior informed consent by the Subjects to participate in the Study. We shall obtain a signed informed consent form (ICF) for all patients prior to their enrollment and participation in the Study in compliance with all applicable laws, regulations and the approval of the (local) Ethics Committee, if required. We shall retain such ICFs in accordance with the requirements of all applicable regulatory agencies and laws.

11. Data Handling

We shall treat all information and data as confidential and shall not disclose such information to any third parties or use such information for any purpose other than the performance of the Study. The collection, processing and disclosure of personal data, will comply with applicable personal data protection and the processing of personal data (the European General Data Protection Regulation of May 25, 2018). We will protect the data

Tear film SARS-nCoV-2 detection in symptomatic and pauci-symptomatic patients.

from disclosure outside the research according to the terms of the research protocol and the informed consent document. The subject's name or other identifiers will be stored separately from their research data and replaced with a unique code to create a new identity for the subject.

12. Data Management

The questionnaires will be collected by Websurveyserver KU Leuven and all data will be stored in on a secured database named Redcap, which is protected within the firewall of the University Hospitals Leuven, Belgium with a unique pseudonymised identifier for every subject. In the future, these data could also be used for related projects.

13. Publication Policy

Any publication will be submitted to all co-authors at least thirty (30) days prior to submission or disclosure.

14. Financial Aspects

No commercial conflict of interest is related to this study. There will be no financial compensation for the volunteers.

15. References

2. World Health Organization. Coronavirus disease 2019 (COVID-19) Situation report - 51 [Internet]. 2020. Available from: <https://www.who.int/emergencies/diseases/novel-coronavirus-2019/situation-reports>
5. Johnlee Varghese. New COVID 19 symptom: Eye pain too could be one of Coronavirus symptoms, says data scientist based on Google Trends [Internet]. 7 April. 2020. Available from: <https://www.ibtimes.sg/new-covid-19-symptom-eye-pain-too-could-be-one-coronavirus-symptoms-says-data-scientist-based-42522>

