Protocol Full Title:

Tear film SARS-nCoV-2 detection in symptomatic and pauci-symptomatic patients.

Protocol Acronym/short title:

Eye-COVID

Version and date of protocol:

V8.0 dd 16-09-2020

Principal Investigator:

Name: dr. [name]

Address: UZ Leuven campus Gasthuisberg, Ophthalmology Department, [name]

[contact]

Email: [contact]

Contact:

[figure not shown]
Name: dr. [name]

Address: UZ Leuven campus Gasthuisberg, Ophthalmology Department, [name]

[contact]

Email: [contact]

Signature Principal Investigator

[name] MD

Principal Investigator

Date: 16-09-2020

Tear film SARS-nCoV-2 detection in symptomatic and pauci-symptomatic patients.

Eye-COVID V8.0 dd 16-09-2020

Pagina 1 van 23

[figure not shown]
Protocol approved by

Prof. dr. [name] MD PhD
Head of the Department of Ophthalmology
(Sub Investigator)

[figure not shown]
[name], MD
(Sub Investigator)

[name] MD PhD
(Sub Investigator)

[name] [name] MD PhD
(Sub Investigator)

Tear film SARS-nCoV-2 detection in symptomatic and pauci-symptomatic patients.

Apotheker klinisch bioloog [name]
(Sub Investigator)

A handwritten signature in blue ink, appearing to read "[name]".

[name] PhD
(Counseling Sub Investigator)

Tear film SARS-nCoV-2 detection in symptomatic and pauci-symptomatic patients.

Eye-COVID V8.0 dd 16-09-2020

Pagina 3 van 23

Title of clinical trial	Tear film SARS-nCoV-2 detection in symptomatic and pauci-symptomatic patients.
Protocol Short Title/Acronym	Eye-COVID
Funding	R95328
Principal Investigator	Dr. [name]
Sponsor	University Hospitals Leuven [name]
Sponsor Reference Number	S 64002
Purpose of clinical trial	To investigate the presence of SARS-nCoV-2 in the tear film of symptomatic and pauci-symptomatic SARS-nCoV-2 positive patients.
Trial Design	Exploratory study using biological samples
Summary of eligibility criteria	
 • ≥ 18 years old. • Willing to undergo sampling of the conjunctiva. • Willing to fill in a questionnaire. • Fluent in written and verbal Dutch. • Capable of giving informed consent. • Part 1 only: positive test for SARS-nCoV-2 on a nasopharyngeal swab.

Tear film SARS-nCoV-2 detection in symptomatic and pauci-symptomatic patients.

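### Symptom correlations are a primary outcome with no sizing, every test counts at P ≤ 0.05, and no single tear result per patient is defined: label the outcome exploratory, test one named symptom, and use the first sampling day

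*Combined protocol and SAP*

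**What the plan says.** Section 2 lists two primary outcome measures. The first is presence of the virus in the tear film. The second is "Correlations between SARS-nCoV-2 in the tear film and mild (like anosmia, ageusia, upper and lower respiratory tract infection) or severe symptoms", with pneumonia and need for hospitalization as examples of severe symptoms.

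Section 7.1 opens "Although this is a pilot study" and bases the sample size on a population count, "with a confidence interval of 5 and a confidence level of 95" per cent. It prints no resulting number of participants, and it gives no effect size, power or expected tear positivity.

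Section 7.2 sets a general rule: "All statistical test will be significant if the P-value" is at most 0.05. Under primary outcomes it says "The presence or absence of the virus in the tears is the primary objective", followed by "A multivariate analysis will be used to interpret the questionnaire". It names no model, tested predictor, hierarchy or adjustment, and does not say which tear result counts for a patient with several.

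Addendum A has 16 yes/no symptom items. Section 4.1 has Part 1 swabbed every three days up to discharge and Part 2 swabbed once. The synopsis describes the design as "Exploratory study using biological samples". Section 1 singles out one association in advance: "A correlation between anosmia and a positive PCR in the tear film is suspected".

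**The concern.** An outcome ranked as primary would normally have a sample-size basis, a defined endpoint and a stated set of tests. Outcome 2 has none of these, yet any test on it may be called significant at 0.05. The anosmia hypothesis, for which Section 1 gives an anatomical reason, would be read beside 15 other items at the same threshold. A chance result on any of them could then be reported as a primary finding.

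The second problem is the endpoint. Part 1 patients are admitted with COVID-19 and swabbed repeatedly. Part 2 participants have mild symptoms and are swabbed once. If a patient counts as positive when any swab is positive, the more severely ill group has more chances to be positive by design, and the result could be mistaken for a link with severity.

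**Working it through.** **What 7.1 sizes.** The inputs fit n = z²p(1−p)/d². Section 7.1 does not state p; 0.5 is assumed.
- If 5 means ±5 points: 1.96² × 0.25 / 0.05² = 384.2, so 385.
- If 5 points is the full width: 1.96² × 0.25 / 0.025² = 1,536.6, so 1,537.

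There is no printed n to reproduce. On either reading the formula concerns one proportion, which is outcome 1. Nothing in it bears on an association.

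**Number of items (Addendum A).** Smell, taste, red eye, eye irritation or pain, tearing, purulent secretion and runny nose make 7. Blocked nose, cough, breathlessness, chest pain, fever, muscle pain, headache, diarrhoea and abdominal pain make 9. The total is 16. None asks about pneumonia or hospitalization, so the one sentence on the questionnaire does not reach all of outcome 2.

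**Chance of at least one false association, no true association, each test at 0.05.**
- 16 independent items: 1 − 0.95^16 = 56.0%; expected number 16 × 0.05 = 0.8.
- Four independent groupings: 1 − 0.95^4 = 18.5%.
- One test: 5%.
- 16 separate tests with equally correlated statistics (200,000 simulated sets): 47.6% at correlation 0.3, 37.4% at 0.5, 26.3% at 0.7.
- 16 coefficients in one joint model, at predictor correlations from 0 to 0.7: 55–56%.

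A finite-sample check simulated 385 patients with 16 binary items, each present in 30% (assumed). Latent item correlation ran from 0 to 0.5 and tear positivity from 5 to 50% (both assumed), with 1,500 runs per setting. It gave 45–60% for a joint logistic model and 45–56% for separate chi-square tests.

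**Unequal swabbing.** Assume 10% positivity per sampling day in both parts, and three Part 1 sampling days (at three-day spacing, six days from first to last).
- Part 2, one day: odds 0.10/0.90 = 0.111.
- Part 1, independent days: 1 − 0.9³ = 27.1%; odds 0.271/0.729 = 0.372; odds ratio 0.372/0.111 = 3.3.
- Part 1, within-patient correlation 0.6 (beta-binomial with a = 0.1 × 0.4/0.6 = 0.0667 and b = 0.9 × 0.4/0.6 = 0.6): the chance of no positive day is (0.6 × 1.6 × 2.6)/(0.667 × 1.667 × 2.667) = 0.842, so 15.8% ever positive; odds 0.187; odds ratio 0.187/0.111 = 1.7.

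The true odds ratio in this set-up is 1. The excess comes only from the number of swabs.

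**The case against.** The strongest reply is that no passage says 16 items will each be tested. Section 1 says the questionnaire is for seeking correlations with disease stage (including routine blood results), ocular symptoms, and anosmia or ageusia. Read as four groupings, the risk is 19%. A global test or a composite would not inflate it at all, and strongly correlated symptoms tested one by one would lower it. This stands: the 56% is conditional on an item-by-item reading, and the inclusion of blood results leaves the number of tests open.

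The study also calls itself exploratory in the synopsis and the heading of 2.1, and a pilot in 7.1, and 7.2 names a single primary objective. That softens the consequence. It does not remove the problem, because Section 2 still ranks the correlations as primary and 7.2 attaches significance to every test without calling any of them exploratory.

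A reader might infer three stronger points. The documents support none of them.
- *Outcome 2 is underpowered.* No tear positivity is given. With 385 positives, a symptom present in half and an odds ratio of 2 (all assumed), power for one symptom tested alone is 30%, 51% and 80% at assumed positivity of 5, 10 and 23%. The answer follows from the assumption.
- *The model would break down, so a penalised method is required.* In simulation at 385, with positivity of 5–23%, at most 0.5% of 16-item fits were unusable. Firth penalisation is a reasonable option, not a correction.
- *The population figure in 7.1 undermines this outcome.* It has almost no effect on the sizing of outcome 1 and no bearing on outcome 2.

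Two objections to the fix have weight. Testing only anosmia is a scientific choice that belongs to the sponsor; it is proposed because it is the one association that Section 1 suspects in advance. And a first-day result does not equalise time since onset, since the first Part 1 swab may follow the nasopharyngeal swab by up to three days.

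**Conclusion.** The point holds in a conditional form and should be fixed. Outcome 2 is listed as primary, 7.1 does not size it, and 7.2 allows any questionnaire test to be declared significant at 0.05. If all 16 items are read that way and every null is true, at least one false primary association has probability 56% with independent items, about 55% in a joint model and 26–48% for separate tests with test-statistic correlation 0.7 to 0.3. It is 19% for four independent groupings. These figures do not rest on an assumed tear positivity; they do depend on how many tests are made and in what form.

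The endpoint gap is separate. An ever-positive definition would produce an apparent association with severity, with an odds ratio of about 1.7–3.3 under the stated assumptions. The plan does not say that it will use that definition; it leaves it open.

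Outcome 1 is unaffected.

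**What to change.** **Section 2.** Label outcome 2 exploratory, in line with the synopsis, 2.1 and 7.1.

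**Section 7.2.** Replace the questionnaire sentence, and make the general P ≤ 0.05 rule subject to it:

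> Outcome 2 is exploratory. Among participants with a positive nasopharyngeal swab, the tear PCR result of the first sampling day (positive if either eye is positive) will be analysed by logistic regression. Change in smell (Addendum A, first item) is the only symptom tested at P ≤ 0.05. All other items, and severity measures including pneumonia and hospitalization, will be reported as odds ratios with 95% confidence intervals, without claims of significance. Later Part 1 swabs will be used for the secondary outcomes on onset, duration and Ct.

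If the sponsor prefers a different single hypothesis, it should be named in the same place before the data are examined.

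**Section 7.1.** Add that the sizing applies to outcome 1 only.

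**Cost.** Text changes only, with no added patients, visits or swabs. With one tested symptom the false-association risk returns to about 5%. In exchange, other symptoms and severity cannot be declared significant, and Part 1 patients who turn positive after the first day do not count as positive in this one analysis. The change adds no power.
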